2 STUDY DESCRIPTION

2.1 Study Design

This is a Phase 3, open-label, multi-center trial investigating lenalidomide/low-dose dexamethasone with and without elotuzumab in subjects with newly diagnosed, untreated MM. The study population will consist of subjects who:

- are newly diagnosed with symptomatic MM
- have not received any prior systematic anti-myeloma therapy AND
- have measurable disease AND
- are not candidates for high-dose therapy plus stem-cell transplantation (SCT) because of age (≥ 65 years) or coexisting conditions
- Have met all the eligibility criteria (outlined in Protocol Section 3.3).

Eligible subjects will be randomized in a 1:1 ratio to receive either lenalidomide/low-dose dexamethasone (Ld) or elotuzumab/lenalidomide/low-dose dexamethasone (E-Ld). The randomization will be stratified as described in [Section 2.2](#). Approximately 750 subjects will be randomized.

Subjects should receive Ld with or without elotuzumab in 28-day cycles until disease progression, unacceptable toxicity, or the subject meets other criteria for discontinuation of study drug (see Protocol Section 3.5), whichever occurs earlier.

Tumor assessments will be conducted every four weeks relative to the first dose of study medication, until disease progression, death or withdrawal of consent. Subjects who discontinue study medication for reasons other than progression e.g. for toxicity, should continue to have tumor assessments until progression, even if they have gone on to receive subsequent anti-myeloma therapy. Subjects will be followed at least every 16 weeks after disease progression for survival and subsequent myeloma therapies. The primary analyses of efficacy endpoints (using European Group for Blood and Bone Marrow Transplant [EBMT] criteria) will be based on a blinded review of tumor assessments by an IRC.

Crossover between the arms is not permitted.

Blood samples for pharmacokinetic (PK) and immunogenicity analysis will be collected in all subjects who received elotuzumab, prior to elotuzumab infusion on Day 1 of Cycles 1 through 4, 6, 9, 12, 15 and 18, every 3rd cycle after cycle 18 (21, 24, 27, etc..) as well as at the end of the study or discontinuation of treatment, and 30-day and 60-day follow-up visits. In addition, serial PK samples including 30 minutes post end of infusion and two hours post end of infusion will be drawn in Cycles 1, 2 and 3.

For full details of the schedule and timing of assessments see Protocol Section 5.

2.2 Treatment Assignment

After a subject's eligibility for randomization is established and informed consent has been obtained, the subject's treatment will be assigned via an interactive voice response system (IVRS). Subjects will be randomized to Ld or E-Ld in a 1:1 ratio. The randomization will be stratified by:

- Stage of disease (International Staging System (ISS) 1 - 2 versus 3)
- Age (< 75 years old versus \geq 75 years old)
- Eastern Cooperative Oncology Group (ECOG) Performance status (0 versus 1 - 2)

and will be carried out via permuted blocks within each stratum.

2.3 Blinding and Unblinding

This is an open label trial. However, in order to maintain equipoise, the study team, including biostatisticians and programmers, will not have access to the randomization codes until the study is completed. Only the DMC and the reporting independent statistical group for the DMC, which is external to BMS, and completely independent from the study team, will be provided with the randomization information prior to the completion of the study.

The formal interim analysis of PFS will be reviewed by the DMC after at least 70% of the target events per IRC have occurred. The DMC will then notify the Sponsor to unblind the PFS data if the pre-specified criterion for statistical significance has been met.

The primary analysis of PFS and tumor response will be based on disease assessments made by the IRC. The assessments will be made retrospectively and the IRC will be blinded to the treatment arms.

2.4 Independent Data Monitoring Committee and Other External Committees

Two independent committees will be established for this study: (i) a DMC and (ii) an IRC.

An independent DMC will be established before the first subject has been treated and will monitor safety throughout the study. The first comprehensive safety review meeting will take place at the same time when 120 subjects have been randomized and followed up for at least 2 months in study

Subsequent comprehensive safety review meetings will take place every eight months after that. In addition, the DMC will be provided with serious adverse event (SAE) tables every four months. The DMC will also review the efficacy and safety data at the interim analyses to make formal decisions on stopping the trial for superiority (see [Section 0](#)). A separate charter will provide further guidance and describe the activities of this committee, including details on the statistical stopping rules.

An IRC will be responsible for reviewing all tumor assessment data to determine the best response and date of progression, based on the EBMT criteria. IRC-determined response and progression will be used in the primary analyses of PFS and ORR. A separate charter describes the activities of this committee.

2.5 Interim Analyses

The independent DMC will review the interim analysis of PFS data after at least 338 (70%) progression events (per IRC) have been observed and all subjects have been randomized. This formal comparison of PFS will allow for early stopping for superiority. The stopping boundaries will be derived based on the O'Brien and Fleming α spending function and will depend on the actual number of events observed at the time of the interim analysis. However, if there were exactly 338 events, the DMC could stop the study for superiority if the p-value were ≤ 0.0148 . The significance level for the final look after 482 events would then be 0.0455.

If more than 338 events have occurred by the time of the interim analysis, different stopping boundaries will be calculated in East v5.1. It should be noted that survival follow-up would continue even if the study were stopped at the interim analysis of PFS for superiority.

In addition, an interim analysis of OS will be conducted at the time both the PFS and ORR analyses are positive. The nominal significance levels for the interim and final survival comparisons will be determined by an O'Brien and Fleming alpha spending function.

3 OBJECTIVES

3.1 Primary

The primary objective of this study is to compare the PFS of E-Ld versus Ld in subjects with newly diagnosed, untreated MM.

3.2 Secondary

The secondary objectives are:

- To compare the objective response rate (ORR) between treatment arms
- To compare the overall survival (OS) between treatment arms.
- To assess PFS rates at 1, 2, 3, 4, and 5 years
- To compare the change from baseline of the means score of pain severity and the change from baseline of the mean score of pain interference using the Brief Pain Inventory - Short Form (BPI-SF) between treatment arms.

[REDACTED]

[REDACTED]

[REDACTED]

[REDACTED]

[REDACTED]

[REDACTED]

[REDACTED]

[REDACTED]

[REDACTED]

[REDACTED]

[REDACTED]

[REDACTED]

[REDACTED]

[REDACTED]

4 ENDPOINTS

The primary endpoint is PFS based on IRC tumor assessments using the primary definition of PFS (see [section 4.1.1.3](#)). Supportive analyses of PFS are:

- [REDACTED]
- [REDACTED]
- [REDACTED]

The secondary endpoints are:

- ORR. The primary analysis will be based on IRC tumor assessments using the EBMT assessment criteria. Supportive analysis of ORR will be based on investigator assessment of best response.
- OS
- Patient-reported Outcomes (BPI-SF)
- PFS rates at 1, 2, 3, 4, and 5 years

4.1 Endpoint Definitions

4.1.1 Progression-Free Survival (PFS)

4.1.1.1 Definition of an Adequate Tumor Assessment

In the analysis of PFS, subjects who do not progress are censored. A non-progressing subject can be censored on the date of a tumor assessment only if there is sufficient information to rule out progression. An “adequate” tumor assessment visit for ruling out progression will require the following information:

- Serum monoclonal paraprotein results, if measurable at baseline, and

- Urine monoclonal paraprotein results, if measurable at baseline

4.1.1.2 Date of Progression or Censoring When Different Components of a Per Time Point Tumor Assessment Conducted at Different Times

As different tumor measurements may be conducted on different days, for instance, the blood draw for serum M-protein may be on a different date than 24-hour urine, the IRC and investigators were instructed to report the earliest date of the measurements associated with that time point for progression. In contrast, if tumor measurements are done on different dates and the subject is being censored, instructions were to report the latest date of the measurements associated with that time point.

4.1.1.3 Primary Definition of PFS

Primary Definition of PFS: PFS, under the primary definition, is the time from randomization to the date of the first documented tumor progression or to death due to any cause, provided progression or death does not occur more than 10 weeks (two or more assessment visits) after the last adequate tumor assessment. Clinical deterioration will not be considered progression.

The following censoring rules will be applied to the primary definition of PFS:

- Subjects who receive subsequent systemic anti-myeloma therapy prior to documented progression will be censored at the date of the last adequate tumor assessment prior to or on the initiation of the new therapy.
- Subjects who have an event (documented progression or death) > 10 weeks (2 assessment visits) after their last tumor assessment will be censored at their last adequate tumor assessment prior to the event.
- Subjects who neither receive subsequent therapy prior to progression nor have a progression event (including death) will be censored at their last adequate tumor assessment.
- In addition, subjects who do not have any post-baseline tumor assessments and who do not die within 10 weeks of randomization will be censored on the date of randomization.

In all cases, if there are no adequate assessments for censoring then the subject is censored on the date of randomization.

4.1.1.4 Secondary Definition of PFS – ITT Definition

Intent-to-Treat (ITT) Definition of PFS: PFS will also be analyzed applying an ITT definition that utilizes all of the data on each randomly assigned subject at the time of the PFS analysis. PFS under the ITT definition will be defined as the time from randomization to the date of the first documented tumor progression or death due to any cause. Clinical deterioration will not be considered progression. A subject who neither progresses nor dies will be censored on the date of their last adequate tumor assessment. A subject who does not have any post-baseline tumor assessments and who has not died will be censored on the date at which they were randomized.

4.1.2 Objective Response Rate (ORR)

Best overall response is determined as the best assessment based on all on-study efficacy data for the subject. Subjects with objective response are subjects with a best overall response on-study of partial response (PR) or better based on EBMT assessment criteria.

ORR is defined as the proportion of subjects with objective response among all randomized subjects.

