5.4.1 Efficacy Assessment

Response criteria according to [Section 5.4.5](#) will be used for the efficacy analyses. For the purposes of this study, all subjects' tumor assessments by SPEP M protein and UPEP M protein

quantification, corrected calcium (calcium and albumin), and serum free light chain (when indicated for CR assessment), should be re-evaluated per the protocol-stated frequency relative to the date of first dose of study drug until disease progression based on the EBMT criteria, irrespective of dose delays or treatment cycle. **If subject does not have documented EBMT-based disease progression as defined in Section 5.4.5.5 (eg, disease progression was determined by sFLC or other non-protocol-defined criteria) at time of study drug discontinuation, then tumor assessments must continue to be performed according to the same schedule described above until disease progression even if a subsequent anti-myeloma treatment is initiated prior to disease progression.** Subjects will be followed every 16 weeks (or more frequently) after disease progression for survival, subsequent myeloma therapy, and development of second primary malignancy.

All efficacy laboratory assessments should be done through the central laboratory, except corrected calcium, and bone marrow assessments for plasma cell percentage and light chain restriction (clonality by IHC or flow cytometry). All bone marrow aspirate and core biopsy samples should be assessed locally. For any SPEP or UPEP assessment performed locally, in lieu of a central lab assessment, (ie, if the subject cannot complete a visit at the study site), M protein absolute quantification (eg, g/dL or g/L for SPEP and mg/24 hrs for UPEP) must be performed. Any laboratory samples analyzed locally, including for efficacy, must be entered on the appropriate CRF as requested by Sponsor to properly assess efficacy per protocol criteria.

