8.3.2 Objective Response Rate

Best overall response is determined as the best assessment based on all study efficacy data for the subject. Subjects with objective response are subjects with a best overall response on study of partial response (PR) or better based on criteria in [Section 5.4.5](#).

Objective Response Rate (ORR) is defined as the proportion of subjects with objective response among all randomized subjects. The main ORR analysis will be based on IRC assessments.

[REDACTED]

[REDACTED]

[REDACTED]

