7.4.5 Subsequent Anti-Myeloma Therapies

The number and percentage of subjects with any subsequent systemic anti-myeloma therapy (2nd line), reason for first subsequent systemic anti-myeloma therapy regimen (Documented progression of disease, Clinical deterioration without documented progression, Maintenance therapy without disease progression or clinical deterioration, Consolidation without documented disease progression or clinical deterioration, or Other) and all subsequent systemic anti-myeloma therapy agents given categorized using the BMS WHO drug dictionary will be presented by treatment group.

The number and percentage of subjects with any second subsequent systemic anti-myeloma therapy (3rd line) and reason for second subsequent systemic anti-myeloma therapy regimen (Documented progression of disease, Clinical deterioration without documented progression, Maintenance therapy without disease progression or clinical deterioration, Consolidation without documented disease progression or clinical deterioration, or Other) will be presented by treatment group.

The number and percentage of subjects with any subsequent surgery, type of first subsequent surgery (Kyphoplasty, Orthopedic surgery, Debulking surgery or Other) will be presented by treatment group.

The number and percentage of subjects with any subsequent radiation therapy will be presented by treatment group.

A by-subject listing of all subsequent surgery, radiation therapy, and systemic anti-myeloma therapy will be provided.

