7.5.5 Analysis of Objective Response

The number and percentage of subjects in each category of best overall response per IRC (stringent complete response [sCR], complete response [CR], very good partial response [VGPR], partial response [PR], minor response [MR], stable disease [SD], progressive disease [PD], or unable to determine [UD]) according to the IRC will be presented, by treatment group. An estimate of the response rate and an associated exact two-sided 95% CI (Clopper and Pearson¹⁴) will be presented, by treatment group. Also, the number and percentage of subjects in each category of best overall response according to the investigator tumor assessment will be presented by treatment group.

The main analysis of ORR will be based on the IRC assessment and will compare the two treatment groups using a CMH test stratified by the same factors used in the analysis of PFS. An estimate of the treatment odds ratio and corresponding two-sided 95% CI will be presented.

The same analysis will be repeated for the best response per IRC but modified for subsequent therapies. For this analysis only subjects with responses before, or on start of subsequent therapy date will be considered responders. The IRC when doing the blinded assessment of response and progression does not have data on subsequent therapy and discontinuation status. For this reason the IRC best response modified for subsequent therapy will be derived programmatically.

A 2-sided, 95% confidence interval for the difference of ORR between treatment arms will be computed for all randomized subjects by the method of DerSimonian and Laird¹⁵ using a fixed-effects model (setting Δ^2 equal to zero), adjusting for the stratification factors. The weighted response rate difference and 95% CI can be determined using the following formula:

$$\hat{\theta} = \frac{\sum_{i=1}^{12} \hat{\theta}_i w_i}{\sum_{i=1}^{12} w_i} \sim N(\theta, 1 / \sum_{i=1}^{12} w_i)$$

where $\hat{\theta}_i$ is the response rate difference of the i^{th} stratum and $w_i = 1/\text{var}(\hat{\theta}_i)$.

Similar analyses will be repeated based on the investigator's assessment of ORR. A cross tabulation of IRC best response versus the investigator best response will be presented, by treatment group. These measures of concordance will be provided:

- Number of subjects with same response divided by number of randomized subjects

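### Should the ORR analysis that opens the OS test stop counting responses once a subject starts new myeloma therapy?

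*SAP*

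**What the plan says.** - **Definition.** SAP 4.1.2 takes the best response over the whole record: "Best overall response is determined as the best assessment based on all on-study efficacy data for the subject". Protocol 8.3.2 agrees: "Best overall response is determined as the best assessment based on all study efficacy data for the subject". Neither stops at the start of new therapy.
- **Follow-up after a switch.** Protocol 5.4.1 requires assessments to continue until EBMT progression, "even if a subsequent anti-myeloma treatment is initiated prior to disease progression". SAP 2.1 says the same of subjects who stop study drug for other reasons, "even if they have gone on to receive subsequent anti-myeloma therapy".
- **Main and repeat analyses.** SAP 7.5.5 makes the IRC-based stratified CMH test the main ORR comparison. It then repeats that analysis with a restriction: "For this analysis only subjects with responses before, or on start of subsequent therapy date will be considered responders". It adds that the blinded IRC "does not have data on subsequent therapy and discontinuation status", so the restricted version is derived by program.
- **The gate.** Under SAP 7.5.11 and Protocol 8.4.2.3, ORR is tested at the two-sided 5% level if PFS is significant, and OS is tested only if ORR is significant.
- **PFS.** The primary definition (SAP 4.1.1.3) censors at the last adequate assessment before or on the start of new therapy. The ITT definition (SAP 4.1.1.4) does not.

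**The concern.** Put together, these provisions let a subject who never responded to the assigned regimen switch early, reach a partial response on other drugs, and count as a responder for the randomized arm. The plan foresees the route. Protocol 5.4.1 mentions stopping because "disease progression was determined by sFLC or other non-protocol-defined criteria", and SAP 7.4.5 lists among the reasons for new therapy "Clinical deterioration without documented progression, Maintenance therapy without disease progression or clinical deterioration". Of those reasons, clinical deterioration is the relevant one; subjects on maintenance may mostly be in response already.

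Primary PFS drops data after a switch and the ORR that gates OS keeps it, with no reason given in the visible text. At stake is whether OS is formally tested: responses to non-study drugs could help to open or close that gate. In an open-label trial the two arms need not switch at the same rate.

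**Working it through.** **1. Which ORR is the gate?** The SAP answers this. Section 4.1.2 defines ORR on all data, 7.5.5 names the IRC comparison on that definition as the main analysis, and 7.5.11 tests ORR. The term on-study in 4.1.2 cannot be read as a hidden cut-off, because 7.5.5 introduces the cut-off as a modification and says the IRC lacks the data to apply it. The text is clear and consistent.

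**2. Does any stated figure depend on the choice?** The documents give no ORR rate, difference or power. The figure behind the gate is OS power: 354 deaths, HR 0.74, stated 80% (SAP 5).

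- Fixed-design power = Φ(√354/2 × |ln 0.74| − 1.96) = 80.9%.
- With one O'Brien-Fleming-type interim at an assumed information fraction of 0.5 to 0.8, it is 80.7% to 80.0%.
- The HR follows from the survival rates: ln 0.677 / ln 0.59 = 0.739.

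The stated figure reproduces. None of N = 750, 482 PFS events, 354 deaths or the alpha levels changes with the ORR version.

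**3. How much could the choice move ORR?** All inputs here except the arm size are assumptions. Let p be the on-therapy ORR and q the share of on-therapy non-responders who switch before EBMT progression and then respond. With 375 per arm (750/2):

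- Observed ORR = p + (1 − p)q.
- Subjects reclassified = 375(1 − p)q.
- Power = Φ((|p₂ − p₁| − 1.96 s₀)/s₁), with s₀ = √(2p̄(1 − p̄)/375) and s₁ = √([p₁(1 − p₁) + p₂(1 − p₂)]/375). This is the unstratified two-proportion test, two-sided 5%.

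Example, 75% vs 83% with q = 0: p̄ = 0.79, s₀ = 0.02975, s₁ = 0.02960, so power = Φ((0.08 − 0.0583)/0.0296) = Φ(0.733) = 0.768.

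| On-therapy ORR, Ld / E-Ld | q, Ld / E-Ld | Observed ORR (%) | Difference (points) | Power |
|---|---|---|---|---|
| 75 / 83 | 0 / 0 | 75.00 / 83.00 | 8.0 | 77% |
| 75 / 83 | 0.02 / 0.02 | 75.50 / 83.34 | 7.8 | 76% |
| 75 / 83 | 0.05 / 0.05 | 76.25 / 83.85 | 7.6 | 74% |
| 75 / 83 | 0.05 / 0.02 | 76.25 / 83.34 | 7.1 | 68% |
| 75 / 83 | 0.02 / 0.05 | 75.50 / 83.85 | 8.4 | 81% |
| 70 / 80 | 0 / 0 | 70.0 / 80.0 | 10.0 | 89% |
| 70 / 80 | 0.05 / 0.05 | 71.5 / 81.0 | 9.5 | 87% |
| 70 / 80 | 0.05 / 0.02 | 71.5 / 80.4 | 8.9 | 82% |
| 70 / 80 | 0.02 / 0.05 | 70.6 / 81.0 | 10.4 | 92% |

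At 75% vs 83% and q = 0.05 in both arms, the reclassified subjects number 375 × 0.25 × 0.05 = 4.7 (Ld) and 375 × 0.17 × 0.05 = 3.2 (E-Ld). Equal q dilutes the contrast slightly, which makes the gate harder to pass. Larger shifts need an assumed imbalance, and they go either way.

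**4. How large is the group?** To be affected, a subject must have no PR on the assigned regimen, switch before EBMT progression, and then hold a PR for at least 6 weeks (Protocol 5.4.5.2). Protocol 3.3 requires measurable M-protein and excludes non-secretory, oligo-secretory and free-light-chain-only disease, which narrows the free-light-chain route. Protocol 3.2.1 encourages investigators unsure about progression to contact the medical monitor before starting another regimen. The number is not documented, but these conditions point to a small group.

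**5. Would the restricted version be a better gate?** It has costs of its own. Responder status would no longer rest on blinded IRC data alone but also on the date of an open-label switch. Partial start dates are imputed (SAP 8.5): to the first of the month, up to 30 days early, or to 1 January, up to about 12 months early, but never before the day after the last dose. If new therapy began while study drug continued, a deviation that SAP 7.2.2 foresees, that lower limit can move the date later instead. If responses are dated at their first assessment, a PR dated before the switch but confirmed on new therapy would still count. SAP 7.5.5 does not say which date applies, and the IRC charter is a separate document.

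**The case for a change.** The strongest opposing case is that the version can decide a close result. Take assumed control ORRs of 60% and 80% and the smallest experimental-arm count that reaches p ≤ 0.05:

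- 225 vs 251 responders: p = 0.049. Four more control responders give p = 0.094; four more experimental responders give p = 0.022.
- 300 vs 321 responders: p = 0.042. The same changes give p = 0.096 and p = 0.014.

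Four subjects are 4/375 = 1.1% of an arm. This arithmetic stands, but it starts from a result placed at the edge of significance, where any rule that reclassifies four subjects would matter, including the restricted rule. It shows sensitivity without showing that one version is right.

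The second argument is alignment: primary PFS removes post-switch data and the gating ORR does not, without a visible explanation. The difference is real. But two endpoints may treat switching differently, and keeping all data for ORR follows the same principle as the planned ITT analysis of PFS. As for a missing reason, parts of the protocol rationale and the SAP efficacy text are blacked out, so one cannot conclude that none was given. A sentence of justification in SAP 7.5.11 would do no harm, but its absence leaves nobody unsure which test is run.

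**Conclusion.** The concern describes the plan correctly but does not identify an error. The main ORR analysis counts all responses, it gates OS, and the version restricted at new therapy is a repeat. That is a choice of what to estimate, on which reasonable statisticians differ. The choice is clearly specified, leaves the type I error of the endpoint as defined intact, and leaves OS with its own 5% sequential test. The restricted analysis uses the same CMH test and appears on the topline list (SAP 8.7), so any influence of later therapy on ORR will be visible.

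The likely size is small and its direction unknown: about 0.4 to 0.5 points and 2 to 3 percentage points of power with equal switching at q = 0.05, and in the unequal cases above a loss of 7 to 9 or a gain of 3 to 4 percentage points of power. These figures rest on assumed response and switching rates, since the documents give neither. Exchanging the two versions would trade one imperfection for another, so the plan can stand as written.
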